10.4.3 ANALYSIS OF THE SECONDARY ENDPOINT(S)

- Proportion of patients achieving spleen response at week 12 in patients with baseline splenomegaly.
 - This will be measured by comparing spleen measurement at day 84 assessment with baseline spleen measurement. Spleen response is defined as 50% reduction in palpable splenomegaly of a spleen that is at least 10 cm at baseline, a spleen that is palpable at more than 5 cm at baseline becoming non-palpable, or, in cases where volumetric evaluation is feasible, a $\geq 35\%$ reduction in spleen volume in patients with a baseline spleen volume > 450 cc. Spleen responses by palpation will need to correlate with a 50% reduction in longest diameter of the spleen by imaging.
 - Only patients with a palpable spleen or spleen volume > 450 cc will be eligible for spleen response
 - Patients with baseline splenomegaly who do not have spleen size assessment performed at day 84 assessment or who have discontinued study drug prior to day 84 assessment will be considered not to have had a spleen response.
- Proportion of patients achieving spleen response at week 24 in patients with palpable spleen at baseline.

- This will be measured by comparing spleen measurement at day 168 assessment visit with baseline spleen measurement. Spleen response is defined as 50% reduction in palpable splenomegaly of a spleen that is at least 10 cm at baseline, a spleen that is palpable at more than 5 cm at baseline becoming non-palpable, or, in cases where volumetric evaluation is feasible, a $\geq 35\%$ reduction in spleen volume in patients with a baseline spleen volume > 450 cc. Spleen responses by palpation will need to correlate with a 50% reduction in longest diameter of the spleen by imaging.
- Only patients with a palpable spleen or spleen volume > 450 cc will be eligible for spleen response
- Patients with baseline splenomegaly who do not have spleen size assessment performed at day 168 assessment or who have discontinued study drug prior to day 168 assessment will be considered not to have had a spleen response.
- Proportion of patients who have a 50% reduction in MPN-SAF TSS from baseline to week 12 in patients with baseline TSS ≥ 10
 - Reduction in MPN-SAF TSS score will be measured by comparing TSS score at day 84 assessment to TSS score on cycle 1 day 1.
 - Only patients with baseline TSS ≥ 10 will be eligible for symptom response.
 - Patients who do not have a TSS score performed at day 84 assessment or who have discontinued study drug prior to day 84 assessment will be considered to not have 50% reduction in TSS.
- Proportion of patients who have a 50% reduction in MPN-SAF TSS from baseline to week 24 in patients with baseline TSS ≥ 10
 - Reduction in MPN-SAF TSS score will be measured by comparing TSS score at day 168 assessment to TSS score on cycle 1 day 1.
 - Only patients with baseline TSS ≥ 10 will be eligible for symptom response.
 - Patients who do not have a TSS score performed at day 168 assessment or who have discontinued study drug prior to day 168 assessment will be considered to not have 50% reduction in TSS.
- Change in TSS from baseline to week 12 in patients with baseline TSS ≥ 10
 - These will be reported as a nominal value calculated by subtracting the TSS on cycle 1 day 1 from the TSS at day 84 assessment. Improvements in TSS will be represented with values less than zero, while progression of symptoms will be represented with values greater than zero.
 - All enrolled patients' baseline TSS ≥ 10 and documented day 84 TSS will be included in this analysis.
 - Patients who do not have a TSS score performed at day 84 assessment or who have discontinued study drug prior to day 84 assessment will not be included in this analysis.
- Change in TSS from baseline to week 24 in patients with baseline TSS ≥ 10
 - These will be reported as a nominal value calculated by subtracting the TSS on cycle 1 day 1 from the TSS at day 168 assessment. Improvements in TSS will be represented with values less than zero, while progression of symptoms will be represented with values greater than zero.
 - All enrolled patients' baseline TSS ≥ 10 and documented day 168 TSS will be included in this analysis.
 - Patients who do not have a TSS score performed at day 168 assessment or who have discontinued study drug prior to day 168 assessment will not be

- included in this analysis.
- Change in TSS from baseline to time of best response in patients with baseline TSS ≥ 10
 - These will be reported as a percent change from the baseline value by subtracting the TSS on cycle 1 day 1 from the lowest TSS score documented for the patient between cycle 2 day 1 and cycle 7 day 1 and dividing the difference by the baseline TSS score. Improvements in TSS will be represented with values less than zero, while progression of symptoms will be represented with values greater than zero.
 - All enrolled patients' baseline TSS ≥ 10 and at least one other documented TSS score after cycle 1 will be included in this analysis.
 - Patients who do not have a TSS score documented at or beyond cycle 2 day 1 will not be included in this analysis.
- Patient's global impression of change (PGIC) at week 12
 - This will be measured using the validated questionnaire wherein patients are asked about the change in their myelofibrosis symptoms since starting on the study. Patients can choose from one of seven potential answers: Very much improved, Much improved, Minimally improved, No change, Minimally worse, Much worse, Very much worse.
 - This will be reportedly qualitatively wherein the number of patients choosing particular answers will be tabulated and frequencies will be reported.
- PGIC at week 24
 - This will be measured using the validated questionnaire wherein patients are asked about the change in their myelofibrosis symptoms since starting on the study. Patients can choose from one of seven potential answers: Very much improved, Much improved, Minimally improved, No change, Minimally worse, Much worse, Very much worse.
 - This will be reportedly qualitatively wherein the number of patients choosing particular answers will be tabulated and frequencies will be reported.

The analysis of binary endpoint including spleen response will be analyzed by the exact binomial distribution. The change of baseline to week 12 or 24 of the continuous variables including patient-reported outcomes (PROs) will be examined by paired-t test or Wilcoxon signed-rank test, as appropriate.

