4.2.2 SECONDARY ENDPOINTS

- To evaluate the safety and tolerability of fedratinib in MDS/MPNs and CNL we will:
 - Measure the frequency, duration, and severity of AEs per CTCAE v.5.0 using information from physical exams, evaluation of changes in vital signs, serum chemistry, and hematology.
 - Determine the proportion of patients experiencing grade ≥ 3 AE as defined by CTCAE v.5.0
- To evaluate the efficacy of fedratinib on splenomegaly in MDS/MPNs and CNL we will:
 - Determine the proportion of patients who have a spleen response at week 12 as per Modified MDS/MPN IWG Proposed Response Criteria or demonstration of $\geq 35\%$ spleen volume reduction.
 - Determine the proportion of patients who have a spleen response at week 24 as per Modified MDS/MPN IWG Proposed Response Criteria or demonstration of $\geq 35\%$ spleen volume reduction.
- To evaluate the efficacy of fedratinib on patient-reported outcomes in MDS/MPNs and CNL we will:
 - Determine the proportion of patients who have a 50% reduction in MPN-SAF TSS from baseline to week 12 in patients with baseline TSS ≥ 10
 - Determine the proportion of patients who have a 50% reduction in MPN-SAF TSS from baseline to week 24 in patients with baseline TSS ≥ 10
 - Measure the change in TSS from baseline to week 12 in patients with baseline TSS ≥ 10
 - Measure the change in TSS from baseline to week 24 in patients with baseline TSS ≥ 10
 - Measure the change in TSS from baseline to time of best response in patients with baseline TSS ≥ 10
 - Measure patients' global impression of change (PGIC) at week 12
 - Measure PGIC at week 24

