10.4 DESCRIPTION OF STATISTICAL METHODS

10.4.1 GENERAL APPROACH

This will be a phase 2 trial to assess the efficacy of fedratinib in MDS/MPN and CNL. Patients with a

diagnosis of MDS/MPN-U, aCML, MDS-MPN-RS-T, or CNL will be enrolled using modified Simon's minimax 2-stage approach.³¹ The primary endpoint of the study is the proportion of patients achieving an objective clinical response at week 24 which is determined based upon the Modified MDS/MPN IWG Proposed Response Criteria.

An interim analysis will be performed after 9 patients have completed their week 24 disease assessment or have discontinued study treatment prior to week 24 to assess for futility. If there are ≥ 3 responses among these 9 patients, an additional 16 patients will be enrolled for a total of 25. This will be sufficient to test our hypothesis that fedratinib will increase the ORR from a historical standard of 30% to 55% using a power of 80% and a one-sided type 1 error rate of 0.05. The null hypothesis will be rejected if 12 or more responses are observed.

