Platelet response
Transfusion independence when previously requiring platelet transfusions of at least a rate of 4 platelet transfusions in the previous 8 wk
Pretreatment $\leq 20 \times 10^9$ /L: increase from $<20 \times 10^9$ /L to $>20 \times 10^9$ /L and by at least 100%
Pretreatment $>20 \times 10^9$ /L but $\leq 100 \times 10^9$ /L: absolute increase of $\geq 30 \times 10^9$ /L
Neutrophil response
Pretreatment $\leq 0.5 \times 10^9$ /L at least 100% increase and an absolute increase $\geq 0.5 \times 10^9$ /L
Pretreatment, $>0.5 \times 10^9$ /L and $\leq 1.0 \times 10^9$ /L At least 50% increase and an absolute increase $\geq 0.5 \times 10^9$ /L
Spleen response
Either a minimum 50% reduction in palpable splenomegaly of a spleen that is at least 10 cm at baseline or a spleen that is palpable at more than 5 cm at baseline becomes not palpable
Symptom response
Improvement in symptoms as noted by decrease of $\geq 50\%$ as per the MPN-SAF TSS scoring <20 were not considered eligible for measuring clinical benefit.¶

*Presence of dysplastic changes, which may be interpreted within the scope of normal range of dysplastic changes, may still exist in the presence of CR as allowed in MDS IWG. Marrow should exhibit age-adjusted normocellularity in CR.

†If there is no significant fibrosis present on the initial bone marrow biopsy, a second biopsy is not required to prove resolution of fibrosis. Grading of fibrosis in measurement of treatment response should be according to the European Consensus System.⁶⁷

‡Given the current lack of a validated tool to assess complete resolution of symptoms in MDS/MPN, "CR with resolution of symptoms" (a complete resolution of disease-related symptoms as noted by the MPN-SAF TSS in presence of CR) will be a provisional category of disease response.

§Loss of cytogenetic burden of disease by (via FISH or classic karyotyping) known to adversely affect prognosis is required to reach complete cytogenetic remission. Decrease in the cytogenetic burden of disease must be by $\geq 50\%$ (via FISH or classic karyotyping) to be indicative of a partial cytogenetic response. Given variability of fluorescent probes used in FISH, cytogenetic normalization via FISH will depend on the performance characteristics of the specific probes used.

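### Section 10.4.3 counts spleens that cannot respond and adds an imaging condition to palpation responses that section 4.2.2 and Appendix F do not have

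*Combined protocol and SAP*

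**What the plan says.** Section 10.4.3 gives three routes to spleen response, the same at weeks 12 and 24:

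- **Route A:** a spleen palpable at 10 cm or more at baseline, with the palpable extent halved.
- **Route B:** a spleen palpable at more than 5 cm at baseline that can no longer be felt.
- **Route C:** where volumetry is feasible and baseline volume is above 450 cc, a volume reduction of at least 35%.

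It then adds, for routes A and B: "Spleen responses by palpation will need to correlate with a 50% reduction in longest diameter of the spleen by imaging".

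The denominator rule, also the same at both visits, begins "Only patients with a palpable spleen or spleen volume" and sets the volume limit at more than 450 cc. Patients with a missing assessment or early discontinuation stay in as non-responders. The week-24 item is headed "spleen response at week 24 in patients with palpable spleen at baseline". The week-12 item, the study summary and section 10.2 refer to baseline splenomegaly instead.

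Section 4.2.2 defines the endpoint as "spleen response at week 24 as per Modified MDS/MPN IWG Proposed Response Criteria or demonstration of" a volume reduction of at least 35%, with no diameter condition. Appendix F gives the palpation limbs, the second being that a "spleen that is palpable at more than 5 cm at baseline becomes not palpable", again with no imaging condition. In Appendix F a spleen response is one way to achieve clinical benefit, which section 10.4.2 counts toward the primary endpoint.

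**The concern.** Two separate faults could distort the secondary spleen proportions.

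First, the denominator is wider than the set of spleens for which section 10.4.3 provides any response route. Patients outside every route are non-responders by construction, whatever the drug does, and they lower the reported rate.

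Second, palpation and imaging measure different lengths. Sections 7.3.2.1, 7.3.3.3 and 7.3.3.5 record the extent below the left costal margin, while section 7.1.15 records the longest dimension of the whole organ. Halving the first does not halve the second. The added sentence therefore changes the cited response definition. Whether a patient counts may then depend on whether a volume could be calculated, and the same spleen at the same visit may be classified differently in the primary and secondary analyses.

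**Working it through.** **1. The plan's own figures.** No rate, power or sample size is stated for spleen response; section 10.4.3 only says binary endpoints are analysed by the exact binomial distribution. The stated design figures belong to the primary endpoint: 30% against 55%, "an additional 16 patients will be enrolled for a total of 25", continuation with at least 3 responses in 9, rejection with at least 12 in 25, "using a power of 80% and a one-sided type 1 error rate of 0.05". The rejection probability is Σ(x = 3 to 9) P[Bin(9,p) = x] × P[Bin(16,p) ≥ 12−x]. It equals 0.0421 at p = 0.30 and 0.8007 at p = 0.55. The primary design reproduces, and nothing below changes it.

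**2. Denominator against routes (section 10.4.3).**

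| Baseline spleen | In denominator | Routes open |
|---|---|---|
| Palpable ≥10 cm | yes | A, B; C if volume >450 cc |
| Palpable >5 and <10 cm | yes | B; C if volume >450 cc |
| Palpable ≤5 cm, volume >450 cc | yes | C |
| Not palpable, volume >450 cc | yes | C |
| Palpable ≤5 cm, volume ≤450 cc or not measured | yes | none |

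The last row can occur. Section 5.1, criterion 4, admits patients on a symptom score above 10 alone. It also admits a spleen palpable at exactly 5 cm, whereas route B needs more than 5 cm.

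With k such patients among n, the maximum attainable rate is (n−k)/n. The documents give neither number. For an assumed n = 15:

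- k = 0: 100%
- k = 1: 14/15 = 93.3%
- k = 3: 12/15 = 80.0%
- k = 5: 10/15 = 66.7%

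Purely for illustration, take the 36.5% that section 2.1 reports for myelofibrosis as the rate among spleens that can respond. The reported rate is then 0.365 × 14/15 = 34.1% with k = 1, and 0.365 × 12/15 = 29.2% with k = 3.

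**3. The diameter condition.** Let P be the palpable length and H the length above the costal margin. Assume the longest diameter lies along the palpable axis, so that it equals H + P. H is not in the documents; I use 4 to 14 cm.

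- *Route A, minimal response.* The cut in diameter is 0.5P/(H+P), below 50% for every H > 0. At P = 10 cm it is 5/14 = 35.7% (H = 4), 5/18 = 27.8% (H = 8), 5/20 = 25.0% (H = 10) and 5/24 = 20.8% (H = 14). At P = 20 cm it runs from 10/24 = 41.7% to 10/34 = 29.4%.
- *Route B, shrinking just to the margin.* The cut is P/(H+P), which reaches 50% only if P ≥ H. At P = 6 cm it is 60.0% (H = 4), 42.9% (H = 8) and 33.3% (H = 12).
- *Palpable reduction needed for a 50% diameter cut:* (H+P)/(2P). At P = 10 cm it is 70% (H = 4), 90% (H = 8), 100% (H = 10) and 110% (H = 12, meaning the spleen must retreat above the margin). At P = 20 cm and H = 10 cm it is 75%.

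**4. Overlap with the volume route.** Section 7.1.15 gives volume as AP × TR × CC × 0.524. If the longest axis halves and the other two change by a factor g, the volume reduction is 1 − 0.5g². That is 50% at g = 1, and it stays at 35% or more until g exceeds √1.3 = 1.14. With uniform halving it is 1 − 0.5³ = 87.5%. So a patient who meets the diameter condition already meets route C, unless the other two axes each grow by more than about 14%, provided volume is available and baseline exceeds 450 cc.

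**5. Who is lost.** Take P = 10 and H = 10 cm, with a minimal route A response and a 25% diameter cut. Under uniform shrinkage the volume falls by 1 − 0.75³ = 57.8%, so the patient counts by route C if baseline volume exceeds 450 cc. If only the length shrinks, volume falls 25% and route C fails too. Under uniform shrinkage the losses are therefore confined to patients with no calculable volume or a baseline of 450 cc or less.

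**6. Primary against secondary.** That same spleen, with no volume available, meets the Appendix F spleen limb (10 to 5 cm) and can count as clinical benefit, subject to Appendix F's other conditions. Under section 10.4.3 it is a non-response.

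**The case against.** A reader might infer that the diameter condition makes the palpation route impossible to meet. The documents do not support that. The answer depends on H, which they do not give. With P = 6 and H = 4 cm, becoming non-palpable is a 60% cut, and a large spleen can qualify with a deep response. The verb *correlate* is also undefined and could be read as supportive imaging rather than a strict threshold.

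A reader might also infer a known, sizeable downward bias. That is not supported either. The number of patients with no response route is not given, and it could be small, since most would have entered on symptoms alone. Section 7.1.15 asks for all three axes to be documented, so complete imaging normally yields a volume. Under uniform shrinkage most minimal palpation responders with baseline above 450 cc would still count through volume.

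Two further points stand. Imaging confirmation of a palpation measure is a reasonable preference in an open-label single-arm study. The differing week-24 heading is minor, because the eligibility rule beneath it is the same at both visits.

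What remains after all this is textual. Section 10.4.3 admits spleens with no response route, and it applies a condition that the endpoint definition and Appendix F lack.

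**Conclusion.** The concern holds in limited form.

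The denominator fault follows from the text alone. Its direction is downward. Its size is k/n of the attainable rate, with k unknown (20% for an assumed 3 of 15).

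The diameter condition is stricter than a minimal route A response for any H > 0, and stricter than a minimal route B response when H exceeds P, assuming the longest diameter lies along the palpable axis. It leaves the palpation route nearly redundant where volume is available and baseline exceeds 450 cc. Its practical effect falls mainly on patients without a calculable volume or with baseline volume of 450 cc or less, and no count of these is available.

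Only the two secondary spleen proportions are affected. Provided clinical benefit is judged by Appendix F as written, the primary endpoint, the 25 patients and the power are unchanged.

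**What to change.** - **Evaluable set.** At both visits, restrict the denominator to spleens that can respond under the stated routes: palpable at more than 5 cm, or volume above 450 cc, at baseline. Use the same population heading at weeks 12 and 24.
- **Definition.** Reconcile sections 4.2.2 and 10.4.3 and Appendix F to one spleen-response definition. Report the analysis by the section 4.2.2 and Appendix F definition. If imaging confirmation is wanted, state exactly what it requires and show that version as a sensitivity analysis. Section 4.2.2 does not repeat the 450 cc baseline limit on the volume route, so the reconciled text should say whether it applies.
- **Reporting.** Give the number of patients with no calculable volume and the number excluded by the narrower denominator.

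The cost is wording in section 10 and a smaller denominator, hence a wider exact interval. As a protocol amendment it needs IRB approval under section 13.2. It is best made before the spleen data are analysed.

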7.3 STUDY SCHEDULE

7.3.1 SCREENING

Screening Visit (Day -30 to 0)

- Obtain and review medical history to determine eligibility based on inclusion/exclusion criteria.
- Written informed consent to be obtained prior to any screening procedures

- Review medications history (including over-the-counter drugs, vitamins, herbs, alcohol) to determine eligibility based on inclusion/exclusion criteria.
- Perform physical examination needed to determine eligibility based on inclusion/exclusion criteria
- Vital signs measurements
- Evaluation of ECOG performance status
- Spleen imaging needed to determine eligibility based on inclusion/exclusion criteria
- Symptom assessment needed to determine eligibility based on inclusion/exclusion criteria
- Serum beta-human chorionic gonadotropin (β -hCG) pregnancy test for women of childbearing potential
- Clinical laboratory testing including serum chemistry, hematology, thiamine level, folic acid, vitamin B12, amylase, lipase, magnesium, phosphorous, uric acid, LDH. Clinical assessments (laboratory tests, spleen imaging) performed as part of the subject's routine clinical evaluation and not specifically for this study need not be repeated after signed informed consent has been obtained provided the assessments fulfill the study requirements and are performed within 30 days of starting study treatment.
- Bone marrow biopsy and aspirate and peripheral blood sample will be performed in order to collect correlative samples. Biopsy must include reticulin stain.
- Cytogenetics
- Next-generation sequencing to assess for mutation involving the following genes: *JAK2*, *MPL*, *CALR*, *TET2*, *DNMT3A*, *ASXL1*, *EZH2*, *SRSF2*, *U2AF1*, *ZRSR2*, *SF3B1*, *RUNX1*, *CSF3R*, *KRAS*, *NRAS*, *CBL*, *PTPN11*, *TP53*, *PHF6*, *IDH1*, *IDH2*, *ETV6*, *SETBP1*

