7.3.2 Cycle 1 Day 1 (Cycle length = 28 days)

7.3.2.1 Baseline Visit (Cycle 1; Day 1)

- Verify patient still meets inclusion/exclusion criteria
- Review results of serum pregnancy test, if applicable
- Assess and record baseline symptoms prior to study drug administration
- Administer MPN symptom assessment form (SAF). This will serve as baseline symptom score.
- Physical exam with documentation of spleen size measured as extent below the left costal margin (LCM) at the mid-clavicular line (measured in centimeters) (e.g. 10 cm below the LCM).
- ECOG performance status assessment
- Record vitals
- Weight
- CBC with differential
- Chemistry profile (sodium, potassium, chloride, creatinine, BUN, total protein, albumin, AST, ALT, alkaline phosphatase, total bilirubin, calcium, CO2)
- LDH, amylase, lipase
- Thiamine level
- C-reactive protein (CRP)
- Administer study treatment and provide medication supply sufficient to reach next protocol-defined visit.
- Provide patient pill and adverse event diary

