10.6 MEASURES TO MINIMIZE BIAS

As this study is a single-arm study randomization is not considered.

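### The week-12 and week-24 TSS-change analyses select patients on the same C1D1 score that they subtract, which biases the mean change towards improvement in expectation

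*Combined protocol and SAP*

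**What the plan says.** Section 7.3.2.1 has the MPN-SAF given at C1D1 and states: "This will serve as baseline symptom score". Section 10.4.3 defines the week-12 change as a value "calculated by subtracting the TSS on cycle 1 day 1 from the TSS at day 84 assessment", with negative values meaning improvement. The analysis set requires "baseline TSS ≥ 10 and documented day 84 TSS will be included in this analysis"; for week 24 it requires "baseline TSS ≥ 10 and documented day 168 TSS will be included in this analysis". Changes "will be examined by paired-t test or Wilcoxon signed-rank test, as appropriate". No alpha, sidedness, power or adjustment is given for these tests. Section 10.6 confirms that there is no comparator: "As this study is a single-arm study randomization is not considered".

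An earlier score also exists. Section 7.3.1 lists at screening a "Symptom assessment needed to determine eligibility based on inclusion/exclusion criteria", and the Schedule of Events (Section 7.3.7) marks MPN SAF TSS at both screening and C1D1. The change analyses do not use the screening score. Section 5.1 admits patients on spleen size and/or TSS above 10, so a patient with a low TSS can enrol on spleen size and then be removed by the C1D1 cut.

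**The concern.** A symptom score varies from visit to visit. If patients are kept only when one reading reaches 10, the group kept has, on average, readings above its own usual level, and the next reading falls back. When that same reading is the baseline, the fall is counted as change on treatment.

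A randomised comparison would largely cancel this, because both arms would drift alike. Here the paired test compares the change with zero, so the drift adds directly to the estimate and raises the chance of a nominally significant improvement. The two endpoints are among those the Study Summary calls important secondary efficacy endpoints, and they support the patient-reported-outcome objective.

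**Working it through.** **The plan's own figures.** The plan states no figure for the TSS analyses. Its one sized design, the primary endpoint, reproduces: continuing with at least 3 responses in 9 and rejecting with at least 12 in 25 gives one-sided alpha 0.0421 at a 30% response rate and power 0.8007 at 55%. It is not in question here.

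**Inputs from the documents.** Cut at TSS 10 on C1D1; baseline C1D1; 25 patients; entry on spleen size and/or TSS above 10; paired test; no control arm.

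**Inputs assumed.** TSS mean μ, SD σ, correlation ρ between visits, the share eligible by spleen, missing data, and a two-sided 5% test (2.5% in the direction of improvement).

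**Formula.** Let B be the C1D1 score and W the later score, bivariate normal with the same mean and SD, and no drug effect. With a = (10 − μ)/σ,

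E[W − B | B ≥ 10] = −(1 − ρ) σ φ(a) / (1 − Φ(a)).

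This is below zero whenever ρ < 1 and the cut removes anyone.

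- μ 15, σ 10, ρ 0.7: a = −0.5; φ/(1 − Φ) = 0.3521/0.6915 = 0.509; −0.3 × 10 × 0.509 = −1.53 points.
- μ 25, σ 10, ρ 0.8: a = −1.5; 0.1295/0.9332 = 0.139; −0.2 × 10 × 0.139 = −0.28 points.
- μ 30, σ 10, ρ 0.7: −0.17 points.

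**Simulation with the entry rule.** Entry on screening TSS above 10 already removes some low scorers, so the simulated bias is a little smaller than the formula gives. With 25 enrolled, half assumed eligible by spleen, scores rounded and bounded at 0-100, independent visit errors, no drug effect and 4,000 runs per case:

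| μ, σ, ρ | C1D1 cut: mean change, false improvement | Screening cut: mean change, false improvement |
|---|---|---|
| 12, 10, 0.5 | −2.70, 20.5% | −0.04, 2.6% |
| 15, 10, 0.7 | −1.24, 10.3% | −0.02, 2.9% |
| 20, 12, 0.7 | −0.97, 6.7% | 0.00, 2.2% |
| 25, 15, 0.7 | −1.05, 6.1% | −0.03, 2.8% |
| 30, 15, 0.85 | −0.27, 3.3% | −0.02, 2.4% |

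The first and last rows lie outside the range quoted in the conclusion and show how it extends. With 15% missing scores added, the C1D1 cut gave −1.83 points and 12.8% (14, 10, 0.6), −2.01 and 9.1% (20, 15, 0.6), and −0.2 and 3.8% (25, 10, 0.8; 40% eligible by spleen).

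The range −0.2 to −2.0 describes the cases tried and is not an outer bound. A low mean with a wide SD gives more: the formula yields −3.59 at 15, 15, 0.6. That normal curve puts Φ(−15/15) = 16% of scores below zero, so it overstates a bounded score, but the bounded figure still exceeds 2 points.

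**If screening and C1D1 errors are not independent.** Suppose the two scores correlate 0.85-0.90 with each other and 0.70 with week 12 (μ 20, σ 12). The plan as written gives −1.1 to −1.2 points, and the screening cut leaves −0.6 to −0.8, with 4.5-5.5% false improvement. The reduction is (1.1 − 0.6)/1.1 = 45% down to (1.2 − 0.8)/1.2 = 33%. At μ 15, σ 10 and correlation 0.65 with week 12, it leaves −1.0 to −1.2 points and 7-9%.

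**If the TSS criterion is re-applied at C1D1.** Section 7.3.2.1 asks staff to verify eligibility again at that visit. If that check uses the C1D1 score, the screening cut still leaves about −0.5 to −0.6 points and 4-5% false improvement.

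**The case against.** A reader might infer that these analyses will show improvement with an inactive drug. The documents do not support that. The bias is in expectation, and with false improvement at 4-14%, some 86-96% of null trials would show no significant improvement. If scores sit well above 10 or are highly repeatable, the drift is a fraction of a point on a 0-100 scale. With no mean, SD or reliability in the documents, only its direction is firm.

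A reader might also take the screening score for an independent second baseline. The documents do not say so. Screening runs from Day -30 to 0, and the form in Appendix C asks about the past 24 hours for fatigue and the past week for other symptoms. Scores taken close together may share the same transient symptom state, and the fix is then only partial.

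The other objections also have weight. These are secondary endpoints with no decision rule, and an uncontrolled open-label change cannot be attributed to the drug under either definition. A stated limitation or a sensitivity analysis on the screening subset would be a defensible minimum. This does not justify keeping a rule that pushes the estimate in the drug's favour when the data for a better one are already scheduled.

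**Conclusion.** The point stands as a bias towards improvement in expectation, confined here to the week-12 and week-24 change endpoints. Its direction follows from the text alone. Its size rests on assumptions: with mean 14-25, SD 10-15, correlation 0.6-0.8 and a two-sided 5% test, about −0.2 to −2.0 points in the cases tried and about 4-14% false improvement against 2.5%. It is negligible with scores well above 10, and larger with a low mean and wide spread or poor repeatability. The primary design figures are unaffected. The best-response TSS endpoint shares the cut and baseline but adds a separate effect by taking the "lowest TSS score documented for the patient between cycle 2 day 1 and cycle 7 day 1"; that is not quantified here. The change is worth making because it is cheap, not because the results would otherwise be unusable.

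**What to change.** - In Section 10.4.3, for the week-12 and week-24 change endpoints, define the symptomatic subset as patients with a screening MPN-SAF TSS of at least 10, and keep C1D1 as the score subtracted.
- Align the wording of these endpoints in the Study Summary and Sections 4.2.2 and 10.2.
- In Section 7.3.2.1, state that the C1D1 eligibility check relies on the screening TSS for the symptom criterion. Otherwise about −0.6 points of bias may remain.
- Report the correlation between the screening and C1D1 scores, so that readers can judge how much of the bias has been removed.

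No new visit, questionnaire or patient is needed. With independent errors the change brings the null mean to within about 0.1 point of zero. With a shared symptom state it removes roughly 30-50% in the cases tried.

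The costs are a slightly less favourable reported mean change, several matching edits, and a subset that differs from the one used for the 50%-reduction proportions unless those are aligned too. Aligning them is reasonable: at mean 12, SD 10 and correlation 0.5, the null response rate was 22.9% with the C1D1 cut and 18.5% with the screening cut, a gap of 4.4 percentage points. At correlation 0.7 and the same mean and SD it was 14.3% against 11.8%, or 2.5 points.
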